5.1.3.2.2 Part 2B, Expansion Cohort

In Part 2B, subjects will receive M8891 at the dose level defined in the Part 2A and cabozantinib at 60 mg QD in 21-day-cycles until disease progression, unacceptable toxicity, withdrawal of consent, or any criterion for withdrawal from the study (see Section 5.5). Both drugs will be taken in the morning under fasted conditions.

In Part 2B, the SMC will continue to monitor the safety, cumulative and unacceptable toxicity of M8891 combined with cabozantinib and may decide by consensus on continuation on the same dose, change in dose (not higher than MTD in Part 2A), or stop of expansion cohort. Unacceptable toxicity in Part 2B is defined as an AE that meet the DLT criteria (as defined in Section 5.1.3.3) regardless of when they occur while on treatment. Once an MTD or RDE of M8891 combined with cabozantinib has been defined in Part 2A (Section 5.1.3.2.1), enrollment into part 2B may proceed. If less than 6 subjects have been treated at the MTD / RDE selected in Part 2A, there will be an SMC meeting after the first 3 subjects have been treated in Part 2B at the MTD / RDE once these subjects have finished their DLT period or have dropped out, in order to additionally evaluate safety and tolerability at this dose. Enrollment will be suspended for this SMC. The SMC will also meet to evaluate the safety and tolerability of the combination therapy after 10 and 20 subjects have finished their DLT period or dropped out for cumulative and unacceptable toxicity. Enrollment will continue during preparation of these SMCs.

The SMC decisions in the expansion cohort will also be supported by a 2-parameter Bayesian logistic regression model. For details on the model, see Section 8.5.

Dose management of cabozantinib in Part 2B will be at the Investigator's discretion based on clinical judgement. The Investigator must refer to study protocol or M8891 dose modification and to USPI for cabozantinib (see also Section 5.1.3.5).

5.1.3.3 Dose-Limiting Toxicities

DLTs will be used to determine dose escalation and de-escalation as well as determination of MTD. A DLT is any Grade ≥ 3 non-hematologic AE or any Grade ≥ 4 hematologic AE according to the National Cancer Institute – Common Terminology Criteria for AEs (NCI-CTCAE) version 4.03, occurring during the DLT observation period (Cycle 1) that is judged not to be related to the underlying disease or any previous or concomitant medication. DLTs, along with other safety information (including AEs assessed as not related to the underlying disease or other concomitant medications), will also be used to determine RP2D for M8891 as single agent (Part 1) and the RDE/MTD for M8891 combined with 60 mg of cabozantinib QD (Part 2A).

- DLTs are defined as any of the following pre-defined set of AEs observed in the first treatment cycle for Part 1 (21 days) and Part 2A (22 days; 21 days of M8891 combined with cabozantinib, preceded by 1 day of M8891 single agent) based on predefined set of AEs and judged to be M8891 (or M8891 combined with cabozantinib) related or clinically relevant, (excluding events to be related to underlying disease, medical history or concomitant medications/ procedures in the opinion of the SMC).
- Any death not clearly due to the underlying disease or extraneous causes
- A treatment-emergent AE (TEAE) attributable to study drug that in the opinion of the SMC is of potential clinical significance such that further dose escalation would expose subjects to unacceptable risk
- Evidence of treatment related hepatocellular injury, e.g. alanine aminotransferase or aspartate aminotransferase (ALT/AST) $> 3 \times$ upper limit of normal (ULN) with elevation of serum total bilirubin to $> 2 \times$ ULN, without initial findings of cholestasis (elevated serum alkaline phosphatase) or other apparent clinical causality, including liver metastasis
- Any Grade 4 liver enzyme elevation that is possibly drug related should be considered a DLT. In case of Grade 3 or 4 values, the subject must be monitored until recovery to \leq Grade 2
- Grade 4 neutropenia lasting > 5 days or Grade ≥ 3 neutropenia with fever (temperature of $> 38.3^{\circ}\text{C}$)
- Grade 4 thrombocytopenia lasting > 5 days or Grade ≥ 3 thrombocytopenia with clinically significant bleeding
- Any treatment interruption > 7 days or $> 30\%$ of total dose in Cycle 1 due to AEs not related to the underlying disease or concomitant medication
- Any Grade ≥ 3 non-hematologic toxicity **excluding:**
 - Grade 3 nausea or vomiting that lasts < 48 hours, and resolves to \leq Grade 1 either spontaneously or with conventional medical intervention
 - Grade 3 fatigue ≤ 3 days

- Grade 3 hypertension in the absence of maximal medical therapy
- Grade 3 rash \leq 3 days
- Grade 3 electrolyte abnormality that lasts $<$ 72 hours, is not clinically complicated, and resolves spontaneously or responds to conventional medical intervention
- Grade \geq 3 single lab value increase without clinical correlate.

In addition, any TEAE that impairs daily function or considered clinically significant abnormality involving a study subject receiving M8891 (monotherapy or combined with cabozantinib) occurring any time during the study, may be assessed as a DLT.

Subjects screened and eligible for the subsequent cohort will be treated with M8891 (or M8891 combined with cabozantinib) only after a formal SMC decision to proceed to the next dose level has been documented.

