5.1.3.5 Dose Modification

5.1.3.5.1 M8891

In Cycle 1 dose escalation Part 1 and Part 2A, dose modification is not allowed. After completion of the DLT period in subsequent cycles of Part 1 and Part 2A and in all cycles of Part 2B, if Grade \geq 3 non-hematological AEs (for exceptions see 5.1.3.3 Section) or Grade \geq 4 hematological AEs occur but they recover to Grade 1 in \leq 14 days of treatment interruption, and in the absence of disease progression, the subject may continue treatment at a lower dose i.e., 1 level below the current dose or a dose defined by the SMC. If indicated, a further dose reduction is possible.

In Part 1, if a subject does not tolerate the lower dose, the subject will be withdrawn from the trial, In Part 2A, if a subject does not tolerate the dose of 20 mg M8891, the subject will be withdrawn from the trial (see Section 5.5). AEs assessed by the Investigator to be exclusively related to the

subject's underlying disease or medical condition/concomitant treatment are not applicable to the guidelines for dose modification.

The following dose modification guideline in Cycle 2 and subsequent cycles is recommended (Table 8).

Table 8 Recommendation to the Investigator for M8891 Dose Adjustment Based on Non-hematological Adverse Events

CTCAE v. 4.03 Grade	Guideline for Management	Dose Adjustment
1	No intervention	None
2	Treatment as appropriate according to PI's judgment	Dose reduction can be considered after discussion with the medical monitor or SMC decision.
≥ 3	Treatment as appropriate according to PI's judgment	Treatment held until Grade 1 after ≤14 days, then the subject may continue treatment at a lower dose i.e., 1 level below the current dose or defined by SMC.

PI: Principal Investigator.

Guidelines for the management of specific AEs are provided in Section 6.5.5.

In the case of M8891 dose modifications, the SMC might modify the SoA based on emergent data (e.g. PK sampling, if the dose must be adjusted).

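### Protocol 5.1.3.3 defines hematologic DLTs twice, and a short, uncomplicated Grade 4 neutropenia or thrombocytopenia in Cycle 1 is a DLT under one definition and not under the other

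*Protocol*

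**What the plan says.** Protocol 5.1.3.3 contains two statements of what a DLT is.

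- **Opening sentence.** For blood counts it covers "any Grade ≥ 4 hematologic AE according to the National Cancer Institute" criteria in Cycle 1, provided the event is not attributed to the disease or to other medication. It sets no condition on duration or complications.
- **List.** It begins "DLTs are defined as any of the following pre-defined set of AEs observed in the first treatment cycle for Part 1" (and likewise for Part 2A). Its two graded hematologic items are "Grade 4 neutropenia lasting" more than 5 days, or Grade 3 and above with fever; and "Grade 4 thrombocytopenia lasting" more than 5 days, or Grade 3 and above with clinically significant bleeding.

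The list has no graded item for any other Grade 4 hematologic event, although Section 6.5.5 names anemia and leukopenia among the anticipated toxicities. Such an event, or a short cytopenia, can enter through the list only by a non-graded route. One is the item for an attributable event "that in the opinion of the SMC is of potential clinical significance such that further dose escalation would expose subjects to unacceptable risk". Another is the item on interruption above 7 days or above 30% "of total dose in Cycle 1 due to AEs not related to the underlying disease or concomitant medication". After the list, the closing paragraph adds that "any TEAE that impairs daily function or considered clinically significant abnormality involving a study subject receiving M8891" may be assessed as a DLT.

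Protocol Section 2 gives the SMC the final decision on whether an event is a DLT. Section 8.3.1.1 makes Cycle 1 DLTs the Part 1 primary endpoint.

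**The concern.** A drug-related Grade 4 neutropenia of 5 days or less without fever, or a Grade 4 thrombocytopenia of 5 days or less without significant bleeding, is a DLT by the opening sentence and meets neither hematologic list item. Several actions depend on the answer:

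- **Model input.** SAP 15.1 builds the likelihood on the number of subjects with at least one DLT.
- **The patient.** A DLT ends M8891 (Protocol 5.5.1, and 5.1.3.2.1 for the Part 2A DLT period). Under SAP 18.1, item 312, leaving a subject with a DLT on treatment is an important deviation.
- **Site recording.** Protocol 7.4.1.4 requires an event meeting the criteria to be in the eCRF within 24 hours, so sites must apply the definition before any committee decision.
- **Evaluability.** Under Protocol 8.4, a Part 1 subject who misses more than 4 days of Cycle 1 stays in the Dose Escalation set only if a DLT occurred.

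The event type is realistic. Protocol 5.1.3.2.1 reports one DLT in the ongoing 60 mg cohort, a Grade 4 thrombocytopenia, without its duration or whether there was bleeding.

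**Working it through.** **Step 1: does anything rank the two rules?**

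| Place | Leans toward |
|---|---|
| Protocol Synopsis and 8.3.1.1: endpoint rests on a pre-defined set of events | List |
| SAP 18.1, items 307 and 308: repeat the more-than-5-day conditions | List (but this SAP was written for protocol version 2.0) |
| Protocol 5.1.3.5.1: "non-hematological AEs (for exceptions see 5.1.3.3 Section) or Grade" 4 or above hematological AEs | Opening sentence: exceptions are attached to the non-hematologic limb only |
| Protocol Section 2: SMC decides each case | Neither: authority without a criterion |

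The balance favors the list, but no sentence narrows or replaces the opening rule. The SMC charter and the SMC analysis plan, which might hold a working convention, are not among the documents.

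**Step 2: what does the choice do to the Part 1 model?** The documents give no figure for this, so the following is an illustration.

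Inputs from Protocol 8.5.3.1 and 8.5.1:

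- Model: logit P(DLT at dose d) = α + exp(β) × log(d/340).
- E(α) = log(0.8/0.2) = 1.386.
- E(β) = log[(log(0.33/0.67) − 1.386)/log(210/340)] = log(−2.094/−0.482) = 1.469. Both means match the printed values.
- Var(α) = Var(β) = 4; Cov(α, β) = 0.2.
- Overdose control: a dose is eligible only if P(DLT rate > 33%) is below 25%.
- Loss: 0 for the target interval, 1 for under- or overdosing, 2 for excessive dosing.

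Assumed data: 0/3 at each of 7, 12, 20 and 35 mg, and 3 subjects at 60 mg, one with the disputed event. The posterior is the bivariate normal prior times the binomial likelihood, summed over a 1601 × 1601 grid.

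| Dose | P(rate > 33%), counted (1/3) | Loss, counted | P(rate > 33%), not counted (0/3) | Loss, not counted |
|---|---|---|---|---|
| 60 mg | 0.115 | 0.719 | 0.003 | 0.985 |
| 70 mg | 0.190 | 0.693 | 0.006 | 0.978 |
| 75 mg | 0.231 | 0.691 | 0.008 | 0.974 |
| 100 mg | 0.425 | 0.768 | 0.0245 | 0.958 |
| 150 mg | 0.665 | 1.055 | 0.084 | 0.945 |

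- **Preset doses only.** Counted: 100 mg fails and the lowest eligible loss is at 60 mg. Not counted: 100 mg passes, and the lowest loss is at 150 mg.
- **Doses off the preset grid.** Protocol 5.1.3.1 allows them. Counted: 70 and 75 mg both pass and both have lower loss than 60 mg.
- **Event not a DLT and the subject leaves the model for missed doses (0/2).** P(rate > 33%) at 100 mg is 0.031, which passes.

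No Part 2A figure is possible: Protocol 8.5.3.2 leaves that prior to the SMC charter.

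**The case against.** **The list governs.** It is introduced as the definition, the endpoint wording points to it, and the SAP deviation items follow it. One can also say that specific text overrides general text. This is the better guess at intent, but it has to be inferred, and it does not settle the other Grade 4 hematologic events, on which the list has no graded item. Section 5.1.3.5.1 is a dose-modification rule for outside the escalation DLT period, so it is only weak evidence the other way.

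**The SMC adjudicates.** This stands in part. The committee can resolve any case and can reach a short cytopenia through its discretionary item. But case-by-case authority is not a criterion, and sites must record and act first.

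**The model effect is softer than 100 mg passing or failing suggests.** This stands. A reader might infer that counting one such event holds the trial at 60 mg for a set number of further cohorts. The documents do not support that: doses between the preset levels are allowed and pass, and under Protocol 8.5.3.1 the SMC may choose a dose other than the one the model suggests.

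**No event is shown to be affected.** This also stands. A reader might suspect that the reported 60 mg thrombocytopenia was classified under the wrong rule, but its duration and any bleeding are not stated.

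A reader might also see the same contradiction in the Grade 3 non-hematologic exclusions. Those are written as exclusions, and Section 5.1.3.5.1 calls them exceptions, so they are best read that way.

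**Conclusion.** The point holds as a contradiction in the definition of the Part 1 primary endpoint, confined to hematologic events. For a drug-related, uncomplicated Grade 4 neutropenia or thrombocytopenia of 5 days or less, the two statements give opposite answers. For other Grade 4 hematologic events, the opening sentence counts them and the list has no graded item. The section also supplies the Part 2 criteria.

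One event can change the model's recommendation on the preset grid: 0.425 against 0.0245 at 100 mg, on either side of the 25% limit. That rests on the printed Part 1 prior and the assumed cohort results. The model is advisory and the documents give no frequency for such events, so neither an escalation delay nor an error in a recorded classification is claimed. It should be fixed because the cost is small and the endpoint, withdrawal and recording all depend on it.

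**What to change.** State one rule, with the exclusion written out. The hematologic list items say only what is included, so a cross-reference to the list would leave short cytopenias caught by the opening sentence.

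1. In the opening sentence of 5.1.3.3, for example: *any Grade 4 or higher hematologic AE, except Grade 4 neutropenia lasting 5 days or less without fever and Grade 4 thrombocytopenia lasting 5 days or less without clinically significant bleeding, which are not DLTs unless the SMC judges otherwise.* Say also that the treatment-interruption item still applies to these events, so that the edit does not create a new conflict.
2. Add a list item for other Grade 4 hematologic AEs. This keeps the opening sentence's threshold and makes the sentence and the list agree.
3. Recheck the Part 1 Cycle 1 Grade 4 hematologic events already recorded, whether or not coded as DLTs, against the single rule. Include the 60 mg thrombocytopenia. Rerun the model if any classification changes.

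The cost is protocol wording and a review of existing records, with no added patients, visits or procedures.

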5.1.3.4 Maximum Tolerated Dose / Recommended Phase II dose (MTD /RP2D)

In Part 1, the MTD for M8891 as single agent will be investigated and the RP2D for M8891 as single agent will be decided by the SMC. At least 6 subjects need to have been treated at the MTD / RP2D. This might necessitate enrolling additional subjects to fulfill this criterion. In Part 2, the MTD/ RDE and the RP2D for M8891 combined with cabozantinib will be defined. The target toxicity level of the Bayesian 2-parameter model is 30%. The-dose-toxicity model will be used to assist the SMC in selecting the MTD by showing the estimated DLT rate per dose and associated variability of the estimates. In Part 2A, at least 3 subjects need to have been treated at the MTD / RDE. If MTD cannot be determined, the SMC may decide to end dose escalation based on safety, PK and/or **C** data (Part 1) or based on safety and/or PK data (Part 2A), and recommended dose for expansion (RDE) will be determined. Once the MTD/RDE of M8891 combined with cabozantinib (see Section 5.1.3.2.1) for a cohort has been identified in Part 2A, enrollment into Part 2B, dose expansion may proceed (Figure 1).

5.1.3.5 Dose Modification

5.1.3.5.1 M8891

In Cycle 1 dose escalation Part 1 and Part 2A, dose modification is not allowed. After completion of the DLT period in subsequent cycles of Part 1 and Part 2A and in all cycles of Part 2B, if Grade \geq 3 non-hematological AEs (for exceptions see 5.1.3.3 Section) or Grade \geq 4 hematological AEs occur but they recover to Grade 1 in \leq 14 days of treatment interruption, and in the absence of disease progression, the subject may continue treatment at a lower dose i.e., 1 level below the current dose or a dose defined by the SMC. If indicated, a further dose reduction is possible.

In Part 1, if a subject does not tolerate the lower dose, the subject will be withdrawn from the trial, In Part 2A, if a subject does not tolerate the dose of 20 mg M8891, the subject will be withdrawn from the trial (see Section 5.5). AEs assessed by the Investigator to be exclusively related to the

subject's underlying disease or medical condition/concomitant treatment are not applicable to the guidelines for dose modification.

The following dose modification guideline in Cycle 2 and subsequent cycles is recommended (Table 8).

Table 8 Recommendation to the Investigator for M8891 Dose Adjustment Based on Non-hematological Adverse Events

CTCAE v. 4.03 Grade	Guideline for Management	Dose Adjustment
1	No intervention	None
2	Treatment as appropriate according to PI's judgment	Dose reduction can be considered after discussion with the medical monitor or SMC decision.
≥ 3	Treatment as appropriate according to PI's judgment	Treatment held until Grade 1 after ≤14 days, then the subject may continue treatment at a lower dose i.e., 1 level below the current dose or defined by SMC.

PI: Principal Investigator.

Guidelines for the management of specific AEs are provided in Section 6.5.5.

In the case of M8891 dose modifications, the SMC might modify the SoA based on emergent data (e.g. PK sampling, if the dose must be adjusted).

5.1.3.5.2 Cabozantinib

The approved dosage of cabozantinib in mRCC is 60 mg once daily without food until the subject no longer experiences clinical benefit or experiences unacceptable toxicity. In Part 2A, cabozantinib will be used at the approved 60 mg free-base equivalent (FBE) daily dosage. After completion of the DLT period in Part 2A and in all cycles of Part 2B, the dose of cabozantinib can be adjusted to 40 mg and then 20 mg to manage AEs (Section 6.5.5). Subjects unable to tolerate a daily dose of 20 mg should discontinue study treatment.

The following should be taken into consideration in decisions regarding cabozantinib dose modifications (reductions or interruption):

- As a general approach all AEs should be managed with supportive care at the earliest signs of toxicity (Table 9 and Table 10). Should this be ineffective, dose reductions or interruptions should be considered to prevent worsening of toxicity.
- The assigned dose for cabozantinib is 60 mg QD. Two dose reduction levels of cabozantinib are permitted (Table 9) if appropriate.
- Dose modification criteria for cabozantinib are shown in Table 10. Dose reductions and/or interruptions should be implemented for unacceptable toxicity. Doses may be modified at any time while on study.

- Dose modifications or interruptions may also occur in the setting of lower grade toxicity than defined in Table 10, if the Investigator feels it is in the interest of a subject's safety and will optimize drug tolerability.
- Interruption of cabozantinib treatment for AEs may occur at any time (except from Cycle 1 in Part 2A) per Investigator discretion. If treatment is interrupted due to AEs for more than 6 weeks, cabozantinib should be discontinued.
- Dose interruptions for reason(s) other than AEs (e.g. surgical procedures) can be longer than 6 weeks but require Sponsor approval. The acceptable length of interruption will depend on agreement between Investigator and the Sponsor.

Table 9 Dose Reductions of Cabozantinib

Assigned dose	First Dose Level Reduction	Second Dose Level Reduction
60 mg cabozantinib oral QD	40 mg cabozantinib oral QD	20 mg cabozantinib oral QD

QD: Once daily.

Cabozantinib should be discontinued if a QD dose of 20-mg cabozantinib (minimum dose) is not tolerated.

Table 10 Dose Modifications of Cabozantinib for Treatment Related AEs

CTCAE v. 4.03 Grade	Recommended Guidelines for Management ^a
1	Add supportive care as indicated. Continue cabozantinib treatment at the current dose level if AE is manageable and tolerable.
2, tolerable and are easily managed)	Continue cabozantinib treatment at the current dose level with supportive care.
2, intolerable and cannot be adequately managed	At the discretion of the Investigator, cabozantinib should be dose reduced or interrupted ^b .
3 (except clinically non-relevant laboratory abnormalities)	Cabozantinib should be interrupted unless the toxicity can be easily managed with a dose reduction and optimal medical care ^b .
Grade 4 AEs (except clinically non-relevant laboratory abnormalities)	Subjects should have cabozantinib interrupted immediately. Discontinue cabozantinib unless the following criteria are met: 
• Subject is deriving clear clinical benefit as determined by the Investigator and agreed by the Sponsor• Toxicity can be managed with a dose reduction following recovery to Grade 1 (or baseline) and optimal medical care

AE: Adverse event.

^a Study treatment dose adjustment is only needed if the toxicity was deemed related to cabozantinib treatment or had an unclear relationship to cabozantinib treatment.

^b It is recommended that dose holds be as brief as possible.

Guidelines for the management of specific AEs are provided in Section 6.5.5.

5.1.3.5.3

Cabozantinib or M8891 Dose Reinstitution

If the subject recovers from his/ her toxicities to CTCAE version 4.03 Grade \leq 1 or to the baseline value (or lower) and the toxicity was unrelated to study treatment, then study treatment may be restarted with no change in dose.

If the subject recovers from his or her toxicities to Grade \leq 1 or to the baseline value (or lower) within 2 weeks and the AE was deemed possibly related to study treatment, then study treatment may be restarted at a reduced dose (see Section 5.1.3.5).

In case of dose reduction, re-escalation of cabozantinib or M8891 to the previous dose is not allowed.

5.1.4

Follow-up

For Part 1, all subjects will complete an End of Treatment (EOT) Visit 30 (\pm 3) days after the last dose of study drug. For Part 2, all subjects will complete an EOT visit within 7 days after the last dose of study drug. For both Part 1 and Part 2, subjects with serious AEs (SAEs) ongoing at EOT Visit must be followed during the safety follow-up by the Investigator until stabilization or until the outcome is known, unless the subject is documented as “lost to follow-up”.

Subjects who tolerate M8891 (or M8891 combined with cabozantinib) without significant clinically relevant toxicities may continue to receive trial treatment, at the Investigator’s discretion or after consultation with the Sponsor’s physician, as long as there is no evidence of disease progression.

5.2

Discussion of Trial Design

This is a 2-part, Phase I/Ib, first in human, multicenter, open-label trial of M8891 single agent in solid tumors and M8891 combined with cabozantinib in mRCC, administered daily.

5.2.1

Dose Selection

5.2.1.1

Part 1, M8891 Single Agent, Solid Tumors

ICH guideline S9 has been considered as the reference guideline for the determination of the first-in-human starting dose, i.e., a dose that is expected to have pharmacologic effects and reasonably safe to use.

Based on the toxicity profile of M8891 administered to rats and dogs in the 2 pivotal 4-week repeat-dose oral toxicity studies, defining NOAELs of 3 mg/kg in rats and 0.75 mg/kg in dogs, the dog was identified to be the most sensitive species (Table 11). The NOAEL of 0.75 mg/kg dose in dogs also corresponded to the highest non-severely toxic dose (HNSTD). According to ICH guideline S9, when the non-rodent is the most appropriate species, 1/6 of the HNSTD is considered an appropriate starting dose. Hence, the proposed first-in-human starting dose for Part 1 of the

study was calculated to be 7.5 mg (rounded to 7 mg)/subject/day. In the first cohorts of subjects with late stage advanced malignancies, this dose will be given as a once daily oral administration.

Table 11 **First in Human Starting Dose Calculated from Results of 4-week Repeat-Dose Toxicity Studies in Rats and Dogs**

Species	Treatment regimen	NOAEL (mg/kg/day)	Safety factor	Starting dose based on NOAEL (mg per subject) ^a
Rat	Daily, oral	3	1/10	18
Dog	Daily, oral	0.75 ^b	1/6	7.5

NOAEL: No observed adverse effect level.

^a Based on the assumption of 60 kg patient.

^b Corresponds to the highest non-severely toxic dose.

This dose is at the lower end of the predicted BED (20 mg QD /subject) and is therefore considered to be pharmacologically active as well as being safe.

A Bayesian two-parameter logistic regression model with overdose control will be used to assist the SMC with dose selection. The model incorporates nonclinical toxicity and observed DLT information from all previously completed dose escalation cohorts to provide a recommended dose for the next cohort. A preselected set of doses are considered by the model, although doses that are not part of the pre-specified set may be chosen as well. Overdose control will be implemented, thus only doses with an estimated probability of less than 25% that the true DLT rate is more than 33% will be recommended by the model. The decision on the next dose is made by the SMC.

